### 9.2.1 Accrual Justification

Fifty patients will be included at phase I/II study completion inclusive of those patients treated as part of the safety lead in. Moffitt Cancer Center in Tampa, FL, will be the primary and lead institution for this phase I/II single arm study. Moffitt sees about 40 patients with ED-SCLC each year, and we estimate that approximately 25% of patients will be eligible for study enrollment. Additionally, we have support to enroll patients at up to 5 additional US academic institutions that see a similar number or more patients with ED-SCLC annually. Accounting for delays in study opening at the onset and for delays due to interim safety and efficacy stopping points as described above, we anticipate completing accrual to our 50-patient study in about 18 months. We expect to accrue approximately 1 or 2 patients per month for the first 6 months, then approximately 4 patients per month for the remaining 12 months.

## 9.3 Populations for Analyses - Data Set Descriptions

- **All Treated Participants:** All participants who received at least one dose of any study medication
- **Biomarker Participants:** All participants with available biomarker data

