All known or suspected sites of disease (including CNS) should be assessed at screening and at subsequent assessments using the same imaging method and technique. If more than one method is used at screening, then the most accurate method according to RECIST 1.1 should be used when recording data and should again be used for all subsequent assessments. Bone scan, PET scan, and ultrasound are not adequate for assessment of RECIST 1.1 response. In selected circumstances where such modalities are the sole modality used to assess certain non-target organs, those non-target organs may be evaluated less frequently. For example, bone scans may need to be repeated only when complete response is identified in target disease or when progression in bone is suspected. Previously treated CNS metastases are not considered measurable lesions for purposes of RECIST 1.1 response. Screening assessments should be performed within 28 days of initiation of radiation therapy. Participants will be evaluated for tumor response outlined in Table 7.4-1 and Table 7.4-2 or more frequently as clinically indicated or per local Standard of Care, until disease progression (or until

discontinuation of study drug in participants receiving study therapy beyond progression), lost to follow-up, withdrawal of study consent, or the study ends. Tumor assessments for all participants should continue as per protocol even if dosing is delayed. Tumor measurements should be made by the same investigator or radiologist for each assessment whenever possible.

As outlined in section 9.4.1, progression free survival will be calculated from the date of patient registration. The baseline scan for RECIST 1.1 response evaluation will be the imaging assessment performed 2 weeks after completion of thoracic radiation and prior to C1D1 of combined ipilimumab/nivolumab. If the patient progresses between pre-treatment imaging and the baseline scan prior to initiation of ipilimumab/nivolumab, this will be considered disease progression according to the defined primary endpoint. In this circumstance, at the investigator's discretion, the patient may elect to receive study drugs beyond progression according to section 6.5.5. Tumor imaging assessments for ongoing study treatment decisions will be completed by the investigator using RECIST 1.1 criteria.

**Table 7.4-1.** Schedule of CT/MRI Tumor Assessments A

Time On Study	Assessment Frequency	Assessment Week (Day 1 of Week Shown)	Assessment Window

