### 7.4.1 Primary and Secondary Efficacy Assessments

The primary endpoint is progression-free survival at 6 months in all participants. The secondary endpoint is overall survival at 1 year.

See Section 9.4 for the definitions of unacceptable toxicity, OS and PFS. Every effort will be made to collect toxicity, survival and imaging data on all participants, including those withdrawn from treatment for any reason, who are eligible to participate in the study and who have not withdrawn consent for additional data collection. If the death of a participant is not reported, all dates in this study representing a date of participant contact will be used in determination of last known date alive.

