## 9.2 Phase I/II Sample Size Determination

We propose a single arm, non-randomized phase I/II study, with the goal to evaluate efficacy compared to historical controls. Slotman et al. [5] reported a 6-month progression-free survival (PFS) of 24% with platinum-based chemotherapy and thoracic radiation therapy. We would propose to pursue a phase III randomized controlled study if there is a 20% improvement in 6-month PFS with the addition of combined immune checkpoint blockade as part of the proposed clinical study. Therefore, this regimen would be considered not worthwhile to pursue if the true 6-month PFS is 24% or less and worth pursuing if the true 6-month PFS is 44% or greater. The trial will use a Simon's 2-stage design[49] with 1-sided 0.05 level type I error and 90% power. The total target sample size is 52 patients. During the 1st stage, 18 patients will be accrued. If 4 or fewer patients have not progressed at 6 months, the study will be closed for futility. However, if at least 5 patients have not progressed at 6 months, then the study will continue to accrue an additional 34 patients. Once the total number of patients has accrued (n=52), then the null hypothesis will be rejected if at least 18 patients have not progressed at 6 months. In order to accommodate censoring, we may increase the total sample size by up to 10% (n=57).

- The final PFS analysis is targeted to occur 6 months after the last participant is enrolled
- The final OS analysis is targeted to occur 1 year after the last participant is enrolled.

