## 9.4 Endpoints

### 9.4.1 Primary Endpoints

**Part I: Safety Run In Phase I:** Unacceptable toxicity status at the end of 13-week safety observation period with unacceptable toxicity defined as:

- Any grade 4 immune related adverse event (irAE),
- Any  $\geq$  grade 3 noninfectious pneumonitis,
- 
- Any grade 3 irAE, excluding pneumonitis, that does not downgrade to grade 2 within 7 days after onset of the event despite optimal medical management including systemic corticosteroids or does not downgrade to  $\leq$  grade 1 or baseline within 14 days,
- Liver transaminase elevation  $> 8 \times$  ULN or total bilirubin  $> 5 \times$  ULN,
- Any  $\geq$  grade 3 non-irAE, except for the following exclusions:
  - grade 3 fatigue lasting  $\leq$  7 days
  - grade 3 endocrine disorder (thyroid, pituitary, and/or adrenal insufficiency) that is managed with or without systemic corticosteroid therapy and/or hormone replacement therapy and the participant is asymptomatic
  - grade 3 infusion-related reaction (first occurrence and in the absence of steroid prophylaxis) that resolves within 6 hours with appropriate clinical management
  - grade 3 or 4 neutropenia that is not associated with fever or systemic infection that improves by at least 1 grade within 3 days.

**Part II: Phase II:** The primary endpoint is 6-month PFS status. PFS is defined as the duration from date of registration to date of first documentation of progression assessed by local investigator or symptomatic deterioration (as defined above) or death due to any cause. Patients last known to be alive without report of progression are censored at date of last disease assessment. For patients with a missing scan (or consecutive missing scans) whose subsequent scan determines progression, the expected date of the first missing scan (as defined by the disease assessment schedule) will be used as the date of progression.

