### **9.5.3 Safety Analyses**

Safety analyses will be performed for all treated participants. Descriptive statistics of safety will be presented using National Cancer Institute (NCI) Common Terminology Criteria for Adverse Events (CTCAE) version 4.0. All on-study AEs, drug-related AEs, SAEs and drug-related SAEs will be tabulated using worst grade per NCI CTCAE v4.0 criteria by system organ class and MedDRA preferred term. The listings by participant will be produced for all deaths, all SAEs, and all AEs leading to discontinuation of study drug. On-study laboratory parameters including hematology, chemistry, liver function, thyroid function, and renal function will be summarized using worst grade per NCI CTCAE v4.0 criteria.

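### The safety set requires a drug dose, so participants given thoracic radiotherapy but never dosed drop out of the adverse-event tables; the efficacy set should also be named

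*Combined protocol and SAP*

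**What the plan says.** Section 9.3 lists two sets. Biomarker Participants are those with biomarker data. All Treated Participants are "All participants who received at least one dose of any study medication". No set is based on registration or on starting radiotherapy.

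Section 9.5.3 states: "Safety analyses will be performed for all treated participants". Section 9.5.2, on efficacy, names no set.

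On what counts as medication, Section 6.5.2 (headed Study Medications) describes nivolumab and ipilimumab only. Table 6-1 and Section 6.1 list the same two products. Radiotherapy has its own Section 5, and the heading of Section 4.6 names it separately from study drug. It is nevertheless the treatment with which participants begin (Section 4.4.1), and it is part of the regimen in the Phase II objective (Section 2.1.2).

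Three statements bear on the efficacy denominator:
- Section 7.4.1: "The primary endpoint is progression-free survival at 6 months in all participants".
- Section 9.4.1: "PFS is defined as the duration from date of registration to date of first documentation of progression".
- Section 7.4: "If the patient progresses between pre-treatment imaging and the baseline scan prior to initiation of ipilimumab/nivolumab, this will be considered disease progression".

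**The concern.** The question the trial puts is whether radiotherapy followed by dual checkpoint blockade is tolerable and active. A safety set that opens only at the first drug dose leaves out anyone who received the first component and stopped there.

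The omission need not be random. Drug must start within 21 days of the end of radiotherapy (Section 4.2), so a participant whose radiation toxicity has not settled, or who deteriorates in the interval, is a natural candidate never to be dosed. Section 1.4 names pneumonitis as the chief worry, and Section 5.9 lists severe radiation reactions as possible. The participants missing from the tables may be among those with the most to report.

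The efficacy analysis has a related but lesser gap. With no set named in Section 9.5.2 and only a drug-treated set in Section 9.3, an analyst could use that set by default. It would remove failures from an endpoint whose clock started at registration.

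**Working it through.** **1. Who is left out of the safety tables.** Radiotherapy takes 10 working days, about 2 weeks (Section 5.2). Drug follows 14 to 21 days later (Section 4.2). So 2 + 2 = 4 to 2 + 3 = 5 weeks pass between the first fraction and the first dose. Adverse events are assessed continuously in that period (Table 7.1-2), and SAEs are collected from consent (Section 8.1.1). A participant who leaves treatment in those weeks has adverse-event data but does not meet the Section 9.3 definition, and Section 9.5.3 tabulates only those who do. The documents give no expected number. As an illustration, five among 52 would leave 52 − 5 = 47 in the tables, omitting 5/52 = 9.6%.

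**2. The plan's design reproduced.** Section 9.2 takes the regimen as "not worthwhile to pursue if the true 6-month PFS is 24% or less" and "worth pursuing if the true 6-month PFS is 44% or greater", with "1-sided 0.05 level type I error and 90% power". The trial stops if 4 or fewer of 18 are progression-free at 6 months, and rejects the null if at least 18 of 52 are. With b the binomial probability,

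P(reject) = sum over x = 5 to 18 of b(x; 18, p) × P(Bin(34, p) ≥ 18 − x).

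- p = 0.24: 0.0494, with probability 0.559 of stopping at stage 1.
- p = 0.44: 0.9035.

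The stated design holds when every accrued participant is counted. (Sections 4.2 and 9.2.1 give 50 rather than 52; that is a separate matter.)

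**3. Undosed failures left out, no replacement.** The rule counts successes among accrued participants. An undosed failure is not a success, so leaving it out changes neither the stage-1 count nor the final count, and type I error stays at 0.0494. The reported rate does move. Ignoring censoring, 18 successes with five undosed failures excluded give 18/47 = 38.3% instead of 18/52 = 34.6%.

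**4. Undosed failures left out and replaced until 52 are dosed.** If a fraction d of registered participants fail before drug and the true rate in all registered is 0.24, the rate among the dosed is 0.24/(1 − d). The fraction d is an assumption.

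| d | rate among dosed | type I error | stage-1 stopping |
|---|---|---|---|
| 2% | 0.2449 | 0.059 | 0.539 |
| 5% | 0.2526 | 0.076 | 0.508 |
| 10% | 0.2667 | 0.115 | 0.453 |
| 15% | 0.2824 | 0.172 | 0.395 |

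Replacement at 10% would need about 52/0.90 = 57.8 registrations. Section 9.2 allows at most 57, and gives censoring as the reason.

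**The case against.** **The term is not closed.** Section 9.3 does not define study medication. The opening of Section 6 says study drugs include non-investigational products, Section 4.2 lists radiotherapy as the first part of the investigational treatments, and Section 4.4.1 calls it study treatment. Treated participants in Section 9.5.3 could be read to include the irradiated. This shows that the intent may be broader than the wording. It does not rescue the wording, because a dose of medication is not a natural description of radiotherapy and Section 6.5.2 uses the term for the two drugs.

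**Radiation harm is captured elsewhere.** It is collected, and the monitoring committee reviews all adverse events monthly (Section 8.8). It can also count toward the lead-in stopping rule, since one of the two start points that Section 4.1 gives for the 13-week window is the start of radiotherapy. This stands: the omission concerns the analysis tables, not collection or oversight.

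**The stronger reading.** A reader might infer that All Treated also governs PFS, so that early failures vanish and type I error is inflated. The documents do not support this. No section assigns that set to efficacy. Sections 7.4.1, 9.4.1 and 7.4 all point to keeping pre-drug failures, and Section 9.2 counts accrued participants. The inflated error rates also need replacement of undosed failures, for which the documents contain no rule. Nor are all pre-drug progressors undosed: Section 6.5.5 lets some go on to drug, and they would be in All Treated with their event counted.

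**Conclusion.** The safety point holds. On the plain reading of Sections 9.3, 6.5.2 and 9.5.3, participants who had radiotherapy but no drug are missing from the adverse-event tables for a regimen that begins with radiotherapy. How many is unknown; the 47-of-52 figure is only an illustration.

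The efficacy point is secondary: a set left unnamed, with the other sections implying all registered participants. Type I error would exceed 0.05 only under exclusion together with replacement (0.076 at an assumed 5% pre-drug loss, 0.115 at 10%). Without replacement the decision is unchanged, and what is at risk is an inflated descriptive rate, 38.3% against 34.6% in the five-participant example.

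**What to change.** - **Sections 9.3 and 9.5.3:** define the safety set as all participants who receive at least one fraction of thoracic radiotherapy or one dose of nivolumab or ipilimumab.
- **Section 9.5.2:** state that the stage-1 count, the final count and the Kaplan-Meier analysis use all eligible registered participants. Pre-drug progression, symptomatic deterioration and death count as failures, and never-dosed participants are not replaced. Registration is the right anchor because the PFS clock starts there; a set limited to those who start radiotherapy would still drop some registered participants.
- **Drug-treated set:** keep it as supportive. It is also useful beside the drug-related adverse-event tables, whose percentages are diluted when undosed participants enter the denominator.

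The cost is wording in three subsections, with no new data and no change to the sample size. The reported PFS and adverse-event rates may be slightly less favourable. If the sponsor thinks of 44% as the rate among dosed participants, counting undosed participants as failures gives 0.44 × 0.95 = 0.418 and power 0.846 at an assumed 5% loss, or 0.44 × 0.90 = 0.396 and power 0.766 at 10%. The sponsor should therefore say which population the 44% describes.

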## 9.4 Endpoints

### 9.4.1 Primary Endpoints

**Part I: Safety Run In Phase I:** Unacceptable toxicity status at the end of 13-week safety observation period with unacceptable toxicity defined as:

- Any grade 4 immune related adverse event (irAE),
- Any  $\geq$  grade 3 noninfectious pneumonitis,
- 
- Any grade 3 irAE, excluding pneumonitis, that does not downgrade to grade 2 within 7 days after onset of the event despite optimal medical management including systemic corticosteroids or does not downgrade to  $\leq$  grade 1 or baseline within 14 days,
- Liver transaminase elevation  $> 8 \times$  ULN or total bilirubin  $> 5 \times$  ULN,
- Any  $\geq$  grade 3 non-irAE, except for the following exclusions:
  - grade 3 fatigue lasting  $\leq$  7 days
  - grade 3 endocrine disorder (thyroid, pituitary, and/or adrenal insufficiency) that is managed with or without systemic corticosteroid therapy and/or hormone replacement therapy and the participant is asymptomatic
  - grade 3 infusion-related reaction (first occurrence and in the absence of steroid prophylaxis) that resolves within 6 hours with appropriate clinical management
  - grade 3 or 4 neutropenia that is not associated with fever or systemic infection that improves by at least 1 grade within 3 days.

**Part II: Phase II:** The primary endpoint is 6-month PFS status. PFS is defined as the duration from date of registration to date of first documentation of progression assessed by local investigator or symptomatic deterioration (as defined above) or death due to any cause. Patients last known to be alive without report of progression are censored at date of last disease assessment. For patients with a missing scan (or consecutive missing scans) whose subsequent scan determines progression, the expected date of the first missing scan (as defined by the disease assessment schedule) will be used as the date of progression.

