### *3. Physical and Laboratory Test Findings*

a) Positive test for hepatitis B virus (HBV) using HBV surface antigen (HBVsAg) test or positive test for hepatitis C virus (HCV) using HCV ribonucleic acid (RNA) or HCV antibody test indicating acute or chronic infection

i) Individuals with a positive test for HCV antibody but no detection of HCV RNA indicating no current infection are eligible

b) Known medical history of testing positive for human immunodeficiency virus (HIV) or known medical history of acquired immunodeficiency syndrome (AIDS)

c) Inadequate hematologic function defined by:

i) Absolute neutrophil count (ANC)  $< 1,000/\text{mm}^3$ .

ii) Platelet count  $< 100,000/\text{mm}^3$ , or

iii) Hemoglobin level  $< 8.0 \text{ g/dL}$

d) Inadequate hepatic function as defined by either:

i) Total bilirubin level  $\geq 1.5$  times the ULN (except patients with Gilbert Syndrome, who are excluded if total bilirubin  $\geq 3$  times ULN), or

ii) AST and ALT levels  $\geq 2.5$  times the ULN or  $\geq 5$  times the ULN if liver metastases are present

e) Inadequate pancreatic function as defined by either:

i) Lipase  $> 1.5$  ULN. Participants with lipase  $> 1.5$  ULN may enroll if there are neither clinical nor radiographic signs of a pancreatitis

ii) Amylase  $> 1.5$  ULN. Participants with amylase  $> 1.5$  ULN may enroll if there are neither clinical nor radiographic signs of a pancreatitis

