#### **6.5.3.4 Discontinuation Criteria**

Treatment with study therapy should be permanently discontinued for the following:

- Any Grade 2 drug-related uveitis or eye pain or blurred vision that does not respond to topical therapy and does not improve to Grade 1 severity within the re-treatment period OR requires systemic treatment
- Any Grade 3 non-skin, drug-related AE lasting > 7 days, with the following exceptions:
  - Grade 3 drug-related uveitis, pneumonitis, bronchospasm, neurologic toxicity, hypersensitivity reaction, or infusion reaction of any duration requires discontinuation
  - Grade 3 drug-related laboratory abnormalities do not require treatment discontinuation except:
    - ◆ Grade 3 drug-related thrombocytopenia > 7 days or associated with bleeding requires discontinuation
    - ◆ Any drug-related liver function test (LFT) abnormality that meets the following criteria require discontinuation:
      - AST or ALT > 8 x ULN
      - Total bilirubin > 5 x ULN
      - Concurrent AST or ALT > 3 x ULN and total bilirubin > 2 x ULN
- Any Grade 4 drug-related AE or laboratory abnormality, except for the following events which do not require discontinuation:
  - Grade 4 neutropenia  $\leq$  7 days
  - Grade 4 lymphopenia or leukopenia
  - Isolated Grade 4 electrolyte imbalances/abnormalities that are not associated with clinical sequelae and are corrected with supplementation/appropriate management within 72 hours of their onset
  - Grade 4 amylase or lipase abnormalities that are not associated with symptoms or clinical manifestations, or radiographic signs of pancreatitis. It is recommended to consult with the Principal Investigator for Grade 4 amylase or lipase abnormalities
  - For Grade 4 endocrinopathy AEs such as adrenal insufficiency, ACTH deficiency, hyper or hypothyroidosis, or glucose intolerance, which resolve or are adequately controlled with physiologic hormone replacement (steroids, thyroid hormones) or glucose controlling agents, respectively, retreatment can be considered after discussion with the Principal Investigator
- Any dosing interruption lasting > 6 weeks from the last dose with the following exceptions:

- Dosing interruptions to allow for prolonged steroid tapers to manage drug-related AEs are allowed. Prior to re-initiating treatment in a participant with a dosing interruption lasting > 6 weeks from the last dose, the Principal Investigator must be consulted

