### 8.1 Serious Adverse Events

A Serious Adverse Event (SAE) is any untoward medical occurrence that at any dose:

- Results in death
- Is life-threatening (defined as an event in which the participant was at risk of death at the time of the event; it does not refer to an event which hypothetically might have caused death if it were more severe)
- Requires in-patient hospitalization or causes prolongation of existing hospitalization (see **NOTE** below)
- Results in persistent or significant disability/incapacity
- Is a congenital anomaly/birth defect
- Is an important medical event (defined as a medical event(s) that may not be immediately life-threatening or result in death or hospitalization but, based upon appropriate medical and scientific judgment, may jeopardize the participant or may require intervention [eg, medical, surgical] to prevent one of the other serious outcomes listed in the definition above.) Examples of such events include, but

are not limited to, intensive treatment in an emergency room or at home for allergic bronchospasm; blood dyscrasias, or convulsions that do not result in hospitalization.

- Potential drug-induced liver injury (DILI) is also considered an important medical event. (See Section 8.6 for the definition of potential DILI.)
- Suspected transmission of an infectious agent (eg, pathogenic or nonpathogenic) via study drug is an SAE.
- Although pregnancy, overdose, cancer, and potential drug-induced liver injury (DILI) are not always serious by regulatory definition, these events must be handled as SAEs. (See Section 8.4 for reporting pregnancies.)
- Any component of a study endpoint that is considered related to study therapy (eg, death is an endpoint, if death occurred due to anaphylaxis, anaphylaxis must be reported) should be reported as SAE (see Section 8.1.1 for reporting details).

NOTE:

The following hospitalizations are not considered SAEs:

- a visit to the emergency room or other hospital department < 24 hours that does not result in admission (unless considered an important medical or life-threatening event)
- elective surgery, planned prior to signing consent
- admissions as per protocol for a planned medical/surgical procedure
- routine health assessment requiring admission for baseline/trending of health status (eg, routine colonoscopy)
- medical/surgical admission other than to remedy ill health and planned prior to entry into the study. Appropriate documentation is required in these cases

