### **8.1.1 Serious Adverse Event Collection and Reporting**

The Investigator Brochure (IB) contains Reference Safety Information to determine expectedness of serious adverse events for expedited reporting. Following the participant's written consent to participate in the study, all SAEs, whether related or not related to the study, must be collected, including those thought to be associated with protocol-specified procedures.

All SAEs must be collected that occur during the screening period and within 100 days of discontinuation of dosing. If applicable, SAEs must be collected that relate to any later protocol-specified procedure. The investigator must report any SAE that occurs after these time periods and that is believed to be related to the

study or protocol-specified procedure. An SAE report must be completed for any event where doubt exists regarding its seriousness. All SAEs must be reported to BMS Worldwide Safety. The BMS SAE form should be used to report SAEs.

If the investigator believes that an SAE is not related to the study, but is potentially related to the conditions of the study (such as withdrawal of previous therapy or a complication of a study procedure), the relationship must be specified in the narrative section of the SAE Report Form.

SAEs, whether related or not related to study drug, and pregnancies must be reported to BMS (as below) and to the study sponsor, Moffitt Cancer Center, through the MCRN coordinating center within 24 hours of awareness of the event. SAEs must be recorded on the SAE Report Form; pregnancies on a Pregnancy Surveillance Form (electronic or paper forms).

To ensure patient safety, each serious adverse event must be reported to the BMS, the PI and to the MCRN coordinating center within 24 hours of the investigational staff's knowledge. All participating sites will report SAEs by completing an SAE report in OnCore, the electronic data capture system. The SAE must be reported by email ([[contact]](mailto:[contact])) to the MCRN within 24 hours of discovery.

The preferred method for SAE data reporting collection is through the eCRF. The paper SAE/pregnancy surveillance forms are only intended as a back-up option when the eCRF system is not functioning. In this case, the paper forms are to be transmitted via email or confirmed facsimile (fax) transmission to both :

**SAE Email Addresses:** [[contact]](mailto:[contact]) , [[contact]](mailto:[contact])

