## **8.6 Potential Drug-Induced Liver Injury (DILI)**

Wherever possible, timely confirmation of initial liver-related laboratory abnormalities should occur prior to the reporting of a potential DILI event. All occurrences of potential DILIs, meeting the defined criteria, must be reported as SAEs (see Section 8.1.1 for reporting details).

Potential drug induced liver injury is defined as:

1. AT (ALT or AST) elevation > 3 times upper limit of normal (ULN)

AND

2. Total bilirubin > 2 times ULN, without initial findings of cholestasis (elevated serum alkaline phosphatase),

AND

3. No other immediately apparent possible causes of AT elevation and hyperbilirubinemia, including, but not limited to, viral hepatitis, pre-existing chronic or acute liver disease, or the administration of other drug(s) known to be hepatotoxic.

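### The Part I liver line leaves out one of the protocol's three liver stop thresholds, so some treatment-ending liver events need not count as unacceptable toxicity

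*Combined protocol and SAP*

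**What the plan says.** Section 9.4.1 defines unacceptable toxicity for the safety run-in. Its liver line reads "Liver transaminase elevation $> 8 \times$ ULN or total bilirubin $> 5 \times$ ULN", with no condition on grade or duration. The other lines depend on grade: grade 4 immune-related events, pneumonitis of grade 3 or above, other grade 3 immune-related events that fail to downgrade in time (to grade 2 within 7 days, or to grade 1 or baseline within 14), and non-immune events of grade 3 or above with four exclusions, none of them hepatic.

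Section 6.5.3.4 governs when a patient must stop. It says "Any drug-related liver function test (LFT) abnormality that meets the following criteria require discontinuation" and lists three criteria: AST or ALT above 8x ULN, total bilirubin above 5x ULN, and "Concurrent AST or ALT > 3 x ULN and total bilirubin > 2 x ULN".

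Section 8.6 builds potential drug-induced liver injury on the same 3x transaminase threshold with "Total bilirubin > 2 times ULN, without initial findings of cholestasis" and no other evident cause. It adds that "All occurrences of potential DILIs, meeting the defined criteria, must be reported as SAEs". Section 8.1 says "Potential drug-induced liver injury (DILI) is also considered an important medical event". Section 8.1.1 has SAEs sent to the manufacturer and to the sponsor "through the MCRN coordinating center within 24 hours of awareness of the event".

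Sections 4.1 and 9.1 use the 9.4.1 count. Among the first 6 patients, 0 or 1 means proceed, 2 means add 3 patients, and 3 or more means close. A running rule closes the study at 3 of the first 9 or above 33%.

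**The concern.** The liver line takes over two of the three liver stop thresholds, unconditionally, and leaves out the combined one. No reason is given. By the protocol's own rules the omitted pattern is serious: it ends study therapy when drug-related, and when it also meets Section 8.6 it must be handled as an SAE. Section 1.4 names liver toxicities among the clinically relevant adverse events of this drug pair.

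The 9.4.1 count is the Part I primary endpoint. It decides whether the study opens to full accrual, and it feeds the running stopping rule. If a mandatory-stop liver event can stay outside it, the lead-in can take a more permissive action than the toxicity seen would suggest. With 6 to 9 patients, one event is enough to do this.

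**Working it through.** **1. Liver criteria side by side.**

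| Criterion | 6.5.3.4 (stop, drug-related) | 9.4.1 liver line | 8.6 (potential DILI) |
|---|---|---|---|
| Transaminase >8x ULN | yes | yes | – |
| Bilirubin >5x ULN | yes | yes | – |
| Transaminase >3x and bilirubin >2x ULN | yes | no | yes, without cholestasis or other evident cause |

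**2. Can another 9.4.1 line catch the pattern below 8x/5x?** No line refers to potential DILI, SAE status or discontinuation under 6.5.3.4, so it depends on class and grade:

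- immune-related, grade 4: counts;
- immune-related, grade 3, not downgrading in time: counts;
- immune-related, grade 3, downgrading in time: does not count;
- immune-related, below grade 3: does not count;
- non-immune, grade 3 or above: counts;
- non-immune, below grade 3: does not count.

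For example, AST at 4x with bilirubin at 2.5x ULN, drug-related and classed as immune-related, ends treatment. It is uncounted if it is below grade 3, or grade 3 and downgrading on time. The documents do not reproduce the CTCAE liver cut-offs, so I do not assign the example a grade.

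**3. Effect on the decision rule, with no assumed rate.**

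| Counted + uncounted | Action as written | Action if all counted |
|---|---|---|
| 1 + 1 of 6 | proceed | add 3 patients |
| 2 + 1 of 6 | add 3 patients | close |
| 2 + 1 of 9 | proceed | close |

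**4. Illustration under assumed rates.** The plan states no operating characteristics for the lead-in, so there is no figure to reproduce. Let each patient be counted with probability p, have only the uncounted liver event with probability u, or have neither. Both are assumptions.

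- P(at least one uncounted event in 6) = 1 − (1 − u)^6. For u = 0.02: 1 − 0.98^6 = 0.114.
- P(action after 6 differs) is the sum of 6!/(a! b! (6−a−b)!) · p^a · u^b · (1−p−u)^(6−a−b) over all a counted and b uncounted for which a and a + b fall in different action bands (0–1, 2, 3 or more).
- P(lead-in passes) = P(X6 ≤ 1) + P(X6 = 2)·(1 − p)^3. At p = 0.10: 0.8857 + 0.0984 × 0.729 = 0.957. With the event counted and u = 0.05, p becomes 0.15: 0.7765 + 0.1762 × 0.6141 = 0.885.

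| Assumed u | At least one in 6 | Action differs, p = 10% | Action differs, p = 30% | Pass probability if counted, p = 10% (95.7% as written) |
|---|---|---|---|---|
| 0.5% | 3.0% | 1.2% | 2.0% | 95.2% |
| 1% | 5.9% | 2.5% | 4.0% | 94.6% |
| 2% | 11.4% | 5.0% | 7.8% | 93.3% |
| 5% | 26.5% | 12.9% | 18.4% | 88.5% |

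**The case against.** The strongest reply is that the two lists are meant to differ. Section 6.5.3.4 protects one patient; Section 9.4.1 drives a decision about the study. They part company elsewhere too: grade 3 neurologic toxicity of any duration ends treatment but, if immune-related, counts only when it fails to downgrade in time. This stands. A reader might infer that 9.4.1 is a faulty copy of 6.5.3.4 and that every mandatory stop should count. The documents do not support that. The hepatic footnote in Appendix 2 also uses only the 8x/5x pair, so a deliberate two-part line fits the text as well. Appendix 2 does call itself general guidance, whereas 6.5.3.4 sets the stop criteria.

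A reader might also infer that such events can never count, or that these patients are unprotected. Neither holds. Grade and persistence bring some of the events into the count. The patient stops treatment, a potential DILI is reported within 24 hours, and the monitoring committee meets monthly to review adverse events and can have an unsafe study closed. What remains is that none of these steps adds the event to the prespecified count.

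Two more points have weight. The rates above are assumed. The nearest context, Section 1.1.3 on the same drug doses in recurrent disease, mentions one discontinuing patient with raised ALT (alongside other abnormalities) and no bilirubin rise. Those patients did not receive this radiotherapy sequence, and the account does not fix a rate. Also, the 9.4.1 list has an empty bullet after the pneumonitis line in the text available to me, so a line could have been lost, although the liver line itself reads as complete.

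**Conclusion.** The gap is real but narrow. It concerns drug-related hepatic events below 8x/5x that meet the combined threshold and fall outside the grade-based lines. The boundary changes follow from the rule alone, provided such a patient occurs when the count is at a boundary. How often that would happen cannot be derived from the documents, so the percentages are illustration only and do not show that the lead-in is likely to mislead. Calling this an error would go too far: no statement in the plan is contradicted. It is a low-cost safety improvement to consider, held with medium confidence because the omission may be deliberate.

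**What to change.** Add to the 9.4.1 liver line: *or drug-related AST or ALT above 3 × ULN concurrent with total bilirubin above 2 × ULN; if either value already exceeded its threshold at baseline, count only if both have risen from baseline.* Apply it to the lead-in and to the running 33% rule, and leave the other lines as they are. If the omission is intended, one sentence giving the reason would do instead.

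The baseline rule is needed because Section 4.4.2 admits patients with liver metastases and transaminases below 5x ULN, and makes an exception on bilirubin ("except patients with Gilbert Syndrome, who are excluded if total bilirubin" reaches 3x ULN). A patient with both conditions could meet 3x/2x on entry.

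The cost is one clause by amendment and a re-check of liver tests already scheduled before each dose (Tables 7.1-3 and 7.1-4). It brings an attribution and a baseline judgement into a line that is now purely numerical. It also raises the chance of expanding or stopping by an amount that depends on the unknown event rate. In the illustration at a 10% counted rate, the pass probability falls by 0.5 percentage points for a 0.5% event rate but by about 7 points for a 5% rate, which is not negligible.
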